We will perform a one-way probabilistic sensitivity analysis to address uncertainty by varying inputs within 10-15%.

Subgroup Analyses: Reliance on CHS data warehouse for measuring healthcare use may miss costs incurred in other health systems. We expect cross-system healthcare utilization to be similar between groups and low overall due to the size and accessibility of CHS in the study region. However, we will repeat analyses within the subgroup of patients enrolled in the ACO managed by CHS (more than 140,000 lives covered in 2018). Within this subset, we will have complete visibility of all healthcare claims within and outside of CHS during the study interval. Data from this group will be informative to health policy given the introduction of the CMS BPCI, a value-based alternative payment model to improve post-acute care for specific hospital diagnoses, including sepsis. Subgroup analyses will also be performed by hospital and patient factors (e.g., hospital length of stay, discharge disposition, comorbidities).

Extrapolated Incremental Cost Effectiveness Ratio. We will build a Markov-type state-transition simulation model using TreeAge (TreeAge Software Inc.) to estimate ICER of receiving STAR. We will use data derived during the study interval and other evidence-based sources to extrapolate cost-effectiveness analyses to 12 months after discharge. This analysis will be conducted to assess benefit from a societal perspective and determine if the intervention costs associated with STAR are offset by any subsequent reduction in morbidity costs (e.g., reduced hospital readmissions) and improvements in mortality. We will estimate the ICER as the incremental costs divided by the incremental QALYs, including a 3% standard discount for costs and outcomes. The intervention group beta weight from the cost model will be divided by the intervention group beta weight from the QALYs model. **Sensitivity Analyses and Uncertainty:** Model parameters will be sampled from their appropriate distributions over 1000 runs. We will vary key costs and effectiveness estimates across the range of plausible values to determine whether cost-effectiveness of STAR is sensitive to changes in specific assumptions made to

inform the baseline analysis. We will also estimate 95% confidence intervals around ICER point estimates using probabilistic analyses and create acceptability curves comparing STAR favorability at various willingness to pay thresholds.

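### The 12-month end point of the extrapolated cost-effectiveness model credits each post-discharge death averted with less than one life-year, and no planned sensitivity analysis varies it; add a lifetime run beside it

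*Combined protocol and SAP*

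**What the plan says.** The combined protocol and SAP, Aim 2, plans two cost-per-QALY analyses. The within-trial ICER covers the study interval and is framed as benefit to the hospital system. The Extrapolated Incremental Cost Effectiveness Ratio subsection adds a Markov state-transition model in TreeAge, which uses trial data and outside evidence "to extrapolate cost-effectiveness analyses to 12 months after discharge".

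On the purpose of that model the plan states: "This analysis will be conducted to assess benefit from a societal perspective". It asks whether STAR's cost is offset by any "subsequent reduction in morbidity costs (e.g., reduced hospital readmissions) and improvements in mortality". On the measure: "We will estimate the ICER as the incremental costs divided by the incremental QALYs", "including a 3% standard discount for costs and outcomes".

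On uncertainty: "Model parameters will be sampled from their appropriate distributions over 1000 runs", and "We will vary key costs and effectiveness estimates across the range of plausible values". Acceptability curves over several willingness-to-pay thresholds follow; no threshold value is given.

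The plan describes no longer horizon, no terminal value for patients alive at month 12, no horizon sensitivity analysis and no reason for stopping at 12 months. It does not say whether added survivors' later costs would count.

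**The concern.** A cost-per-QALY analysis that is meant to value mortality needs a horizon long enough to hold the consequences of a death averted. Here a patient whose death in the 90-day window is prevented, and who is alive at month 12, contributes nothing after that point: neither QALYs nor costs. Mortality is one half of the primary composite and a secondary outcome in its own right, so a mortality benefit is a result the trial hopes for.

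At stake is how the ICER and the acceptability curve read against a threshold. The 1000-run analysis and the one-at-a-time variation act on parameters within the 12-month structure, so the reported intervals would not show how much the conclusion depends on where the model stops. With no effect on deaths, the horizon changes nothing through deaths averted.

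**Working it through.** The documents give no ICER, QALY gain, cost, utility or survival figure, so there is no stated result to reproduce. From the documents come the 12-month horizon, the 3% discount, the ICER definition and the 90-day STAR window. Everything marked *assumed* is not from the documents.

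**1. Maximum credit per averted death.** Undiscounted, a death averted on day t earns at most 1 − t/365 life-years: 1.00 at day 0, 0.877 at day 45, 0.753 at day 90. Discounted back to discharge at 3%, these are 0.985, 0.862 and 0.740. The mean discount factor over 12 months is (1 − 1/1.03)/ln(1.03) = 0.985, so the discount changes a 12-month total by about 1.5%.

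**2. Share of life-years captured.** *Assumed*: death averted at day 45, exponential survival afterwards with mean L years. With r = ln(1.03), h = 1 − 45/365 and k = 1/L + r, life-years are (1 − exp(−kh))/k to month 12 and 1/k over a lifetime.

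| L (years) | To month 12 | Lifetime | Share captured |
|---|---|---|---|
| 1 | 0.577 | 0.971 | 59% |
| 2 | 0.701 | 1.888 | 37% |
| 3 | 0.751 | 2.756 | 27% |
| 5 | 0.794 | 4.356 | 18% |
| 10 | 0.829 | 7.719 | 11% |

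**3. Effect on the ICER.** Let dC be STAR's net cost per patient before the care of added survivors, dm the mortality reduction, u the utility and c the annual care cost of a survivor. Then

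ICER = (dC + dm·LY·c)/(dm·u·LY) = dC/(dm·u·LY) + c/u.

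With constant c and u, only the first term depends on the horizon, so the direction follows the sign of dC. *Assumed*: dm = 0.01, u = 0.65, c = 20,000 USD, L = 5 (so c/u = 30,769).

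| dC (USD) | 12-month ICER | Lifetime ICER |
|---|---|---|
| +500 | 127,635 | 48,428 |
| +200 | 69,515 | 37,833 |
| 0 | 30,769 | 30,769 |
| −100 | 11,396 | 27,238 |
| −200 | −7,977 (dominant) | 23,706 |

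Over dC of 200 to 500, dm of 0.01 to 0.02, c of 10,000 to 20,000 and L of 1 to 10, the 12-month ICER is about 1.2 to 4.3 times the lifetime one. Because dC is positive throughout, that range shows size and cannot test direction.

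If later costs differ from first-year costs, the direction can reverse with dC positive. *Assumed*: dC = 200, dm = 0.02, L = 5, c = 10,000 to month 12 and 30,000 afterwards. At 12 months: (200 + 0.02 × 0.794 × 10,000)/(0.02 × 0.65 × 0.794), about 34,800. Lifetime: (200 + 0.02 × (0.794 × 10,000 + 3.562 × 30,000))/(0.02 × 0.65 × 4.356), about 44,100.

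The general rule, with positive QALY gains before and after month 12, is that extending the horizon lowers the ICER only if the later cost per QALY is below the 12-month ICER.

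**4. Effect on net monetary benefit.** At threshold λ, the part dropped after month 12 is dm × (lifetime LY − 12-month LY) × (λu − c). It is positive exactly when c/u < λ, whatever the sign of dC. *Assumed*: λ = 50,000, c = 20,000, L = 5, dm = 0.01, u = 0.65. The dropped part is 0.01 × 3.562 × (32,500 − 20,000) = 445 USD per patient. With dC = +500 the net benefit goes from −401 to +45, so the sign changes; with dC = −500 it goes from 599 to 1,045. With c = 60,000 (c/u = 92,308) the dropped part is 0.01 × 3.562 × (32,500 − 60,000), about −980, and the 12-month figure would then flatter STAR.

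**The case against.** The strongest reply is that the horizon is declared, so the result is an openly labelled 12-month ICER. It already reaches well past the 90-day window, it suits the cost-offset question, and it limits reliance on outside survival and cost inputs. This is also a secondary aim, with no bearing on the primary outcome or trial conduct. All of that stands, and it is why the 12-month run should be kept.

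A reader might infer something stronger: that stopping at month 12 biases cost per QALY against STAR. The documents do not support this. Truncation removes added survivors' later costs along with their QALYs, and the plan gives none of the figures that fix the direction. A cost-saving STAR is a live case: the subsection asks whether costs are offset, and the Introduction describes the navigation process as having already lowered readmissions and costs. Nor should the 127,635 versus 48,428 contrast be read as a forecast. It combines the highest net cost and smallest mortality effect of the assumed ranges. With dC = 200 and dm = 0.02 the pair is 50,142 versus 34,301, and the larger ratios need long survival in patients selected as high-risk for death.

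What the reply does not remove is the gap between purpose and method. The model is to value "reduced hospital readmissions) and improvements in mortality" from a societal standpoint, yet no planned analysis credits survival after month 12 or shows how far the answer depends on that.

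**Conclusion.** The point holds in conditional form, as a cheap improvement. From the text and arithmetic alone, each post-discharge death averted is credited with less than one life-year, and no stated sensitivity analysis varies the horizon. If STAR reduces deaths, the QALY gain is understated. The ICER is likely overstated when STAR also has a positive net cost and survivors' later cost per QALY is below the 12-month ICER; it can be understated when STAR saves money or later survivor costs are high. Net monetary benefit is understated whenever later cost per QALY is below the threshold.

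The size is not computable from the documents. The 59% to 11% capture rests on an averted death at day 45, exponential later survival with a mean of 1 to 10 years, and 3% discounting. Every dollar figure rests further on assumed cost, utility and mortality effect. An unconditional claim of bias against STAR is not supported.

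**What to change.** Keep the 12-month result. Pre-specify in the SAP a lifetime run of the same TreeAge model that:

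- applies the stated 3% discount;
- takes long-term survival and annual costs of sepsis survivors from external sources, each varied over a stated range;
- assumes no STAR effect on hazards after the observed period;
- is run with added survivors' later costs included and again with them excluded.

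Report the ICER, net monetary benefit and acceptability curve at both horizons. Net monetary benefit matters because the ratio can move against STAR while the value of adopting it rises, as in the cost-saving case above.

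The cost is a changed termination condition, two external inputs and a few sentences of SAP wording. No new patients or data collection are needed, and the plan already allows outside evidence in this model. The downside is that the lifetime figure rests on more external assumptions and will have a wider range, which is why both horizons should be shown.

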All primary and secondary analyses will follow intention to treat approach, such that all patients meeting identical criteria and randomized will be analyzed, regardless of adherence to intervention assignment. This real-world approach will assess intervention effectiveness while limiting selection biases associated with adherence. We will compare the two groups (STAR versus usual care) at baseline for age, sex, race, and comorbidities to assess for balance inferred randomization. The primary outcome is the composite of hospital readmission and mortality at 90 days post hospital discharge. Because hospitals are randomized to STAR in a staggered sequence and the outcome varies at the patient level, we will use a generalized linear mixed-effects model to compare the composite 90-day mortality and readmission primary outcome measure between the intervention conditions, adjusting for clustering effects across multiple levels (e.g., admitting hospital, implementation timing) to include hierarchical data structures. The intervention fixed-effect coefficient will compare STAR versus UC conditions (i.e., UC as reference). We will evaluate covariates for patient (e.g., sex, race, comorbidities, length of stay, discharge disposition [skilled nursing facility, rehabilitation, home]) and organizational factors (e.g., admitting hospital, guideline adherence, urban versus rural setting, implementation timing) to identify any potential differences between study arms. We will include covariates in model if unbalanced between STAR and UC groups. We will also evaluate effect

modification by conducting analyses stratified by these characteristics (e.g., discharge disposition) and by process measures with potential to effect outcomes (e.g., referrals).

Secondary outcomes are described below and will be assessed using the same approach. That is, we will construct generalized linear mixed-effects models, like for the primary outcome analysis, for individual assessments of secondary outcomes and process measures. We will test different distribution parameters to determine the optimal distribution family for each model and outcome variable (e.g., binomial, gamma distributions).

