b. Event rate: We propose to re-estimate the sample size based on the combined 90-day hospital readmission and mortality rates for both patients randomly assigned to STAR and usual care when half of the information is available for the trial (n=2196). We will base the re-estimation on the original 20% relative reduction to determine if more patients are needed to maintain 90% power. We will measure the composite outcome as defined for the primary effectiveness analysis, i.e., we will capture all patients with either

date of death or eligible hospital readmission prior to 90 days post discharge as event-positive.

2. Interim efficacy analysis with 50% information (i.e., 50% of target accrual with 90-day follow up data).

We propose to conduct an interim effectiveness analysis of the primary outcome of composite 90-day hospital readmission and mortality rates once 50% of patients have been accrued and have 90-day outcomes. We will use the Haybittle-Peto procedure with boundary of less than 0.001. No additional interim analyses will be planned until the sample size re-estimation and futility analyses are reviewed and a recommendation is made to continue, stop, or modify the study.

3. Futility analysis/conditional power at 50% complete data information (50% of target accrual with 90-day follow-up data). We propose to conduct a futility analysis at 50% information accrual for the trial. The first futility analysis will be conducted at the same time as the sample size re-estimation based on the drop-out rate. Conditional power is the probability of detecting a difference at the end of the study ($p<0.05$) given the current data trend. We will estimate conditional power under the null hypothesis of no difference, the designed alternative of 20% relative reduction, and the current observed trend. A recommendation would be made to stop the study for futility if the conditional power is less than 0.10 for the designed alternative.

**Aim 2: To assess the cost-effectiveness of virtual nurse navigator-driven STAR program
Within-trial Incremental Cost Effectiveness Ratio.**

We will estimate Incremental Cost Effectiveness Ratio (ICER) of STAR versus UC using data derived during the study interval as a measure of benefit to the hospital system. We will estimate ICER as incremental costs divided by incremental QALYs. The intervention group beta weight from cost model will be divided by the intervention group beta weight from QALYs model.

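### Aim 2 gives the 12-month Markov ICER a regression-coefficient rule that does not fit it, and assigns the within-trial ICER no clear interval reflecting sampling error, hospital clustering or calendar period

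*Combined protocol and SAP*

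**What the plan says.** Aim 2 has two ICERs.

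**Within-trial ICER.** It is defined as incremental costs over incremental QALYs, and the calculation is then given as "The intervention group beta weight from cost model will be divided by the intervention group beta weight from QALYs model". Neither model is described: Aim 2 gives no link, distribution, covariates, hospital effect or period effect. The uncertainty statement that follows is "We will perform a one-way probabilistic sensitivity analysis to address uncertainty by varying inputs within 10-15" per cent.

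**Extrapolated ICER.** "We will build a Markov-type state-transition simulation model using TreeAge"; the horizon is 12 months after discharge and the perspective is societal. The definition is "We will estimate the ICER as the incremental costs divided by the incremental QALYs, including a 3% standard discount for costs and outcomes". The next sentence is "The intervention group beta weight from the cost model will be divided by the intervention group beta weight from the QALYs model". Under Sensitivity Analyses and Uncertainty, in the same paragraph, the plan says "Model parameters will be sampled from their appropriate distributions over 1000 runs" and, later, "We will also estimate 95% confidence intervals around ICER point estimates using probabilistic analyses and create acceptability curves" across willingness-to-pay thresholds.

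Two other places bear on this. The Introduction (item 2) makes trial data on costs, utilization and outcomes the inputs to the Markov model. Statistical Methods, Aim 1, describes mixed models that account for hospital and implementation timing, but for the Aim 1 outcomes; costs and QALYs are not on that list.

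**The concern.** The extrapolated ICER has two calculation rules that do not describe the same operation. The definition calls for differences between strategies in the model's expected 12-month totals. The coefficient rule needs a cost regression and a QALY regression, and none is described for that horizon. Taken literally, it either cannot be applied to cohort-model output or puts a trial-window quantity in place of the discounted 12-month one.

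For the within-trial ICER the gap is in uncertainty. Varying inputs by a set percentage shows how the answer responds to assumptions. It does not show how much the answer could move because 4392 patients in eight hospitals are a sample. The within-trial ICER could therefore be reported with a sensitivity range and no statistical interval, or with an interval that ignores the stepped-wedge design.

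A lesser, conditional point is scale. A ratio of coefficients is a cost per QALY only if both models are additive in dollars and in QALYs, and Aim 2 does not say that they are.

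**Working it through.** The documents give no ICER, cost, QALY, standard deviation or ICC, so there is no planned figure to reproduce. Every cost, QALY, SD and ICC value below is an assumption used for illustration.

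**1. The coefficient rule against the Markov model.**
- A cohort state-transition model returns expected discounted cost and QALYs for each strategy. The ICER is (C_STAR − C_UC)/(Q_STAR − Q_UC). There is no intervention coefficient to divide.
- If patients were simulated individually, regressing simulated cost or QALYs on strategy would return the same mean differences, so the rule would add nothing.
- If the coefficients come from trial data, they cover the trial window and not the discounted 12 months.

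On no reading does the sentence supply the stated quantity by a route the definition lacks. Its wording is nearly that of the within-trial section, which suggests a drafting carry-over.

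**2. What 10-15% variation reflects.** Its width depends on which inputs are varied and by what percentage, not on the number of patients or hospitals. Assume a cost increment of $500.
- Made up of $1,500 programme cost less $1,000 savings: raising the unit cost of care by 15% gives 1,500 − 1,150 = $350, a fall of 30%.
- With savings S, the same change reverses the sign of the increment once 0.15 × S > 500, that is S > $3,333.
- If the usual-care mean is $10,000 and STAR's is $10,500, raising the usual-care mean by 15% gives 10,500 − 11,500 = −$1,000.

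The range can thus be narrow or wide, but in no case is it a sampling interval.

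**3. What sampling error could look like.** A simulation of 4,000 runs per setting used additive models with fixed hospital and period effects. True differences were −$1,000 and 0.005 QALY, cost SD $15,000-25,000, QALY SD 0.05-0.09 and ICC 0-0.05; 80% of hospital-level variance was constant over time, and cost and QALY errors were independent. The standard errors were $786-1,674 for cost and 0.0027-0.0060 for QALYs. The estimated QALY difference was zero or negative in 3% to 19% of runs, where a ratio becomes unstable. This is why a joint cost-QALY method is needed.

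**4. Hospital and period.** Randomization has one of eight hospitals crossing every four months; Sample Size Determination gives 36 months and 4392 patients.
- Periods: 36/4 = 9. Patients per hospital-period, assuming equal cells: 4392/(8 × 9) = 61.
- STAR cells: 1 + 2 + … + 8 = 36, so 36 × 61 = 2196 per condition.
- Unadjusted pooled SE, in SD units: √(1/2196 + 1/2196) = 0.0302.
- Generalized least squares with fixed periods and random hospital: the treatment variance is the corresponding diagonal element of (Σ Z′V⁻¹Z)⁻¹, with V = ICC·J + [(1 − ICC)/61]·I for each hospital.

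| Assumed ICC | SE (SD units) | Ratio to pooled |
|---|---|---|
| near 0 | 0.0395 | 1.31 |
| 0.001 | 0.0430 | 1.43 |
| 0.01 | 0.0498 | 1.65 |
| 0.05 | 0.0510 | 1.69 |

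With an assumed cluster autocorrelation of 0.8, the ratio runs from 1.42 to 2.14 over ICC 0.001 to 0.05. The ratios combine period adjustment, already 1.31 with almost no clustering, and clustering.

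**5. Scale (conditional).** With a log link, the cost coefficient is ln(C_STAR/C_UC), not a dollar difference. Assume a $500 increment, usual-care mean cost of $10,000 to $40,000, and QALYs of 0.150 and 0.153.
- Additive: 500/0.003 = $166,667 per QALY.
- Log cost, additive QALYs: ln(10,500/10,000)/0.003 = 0.0488/0.003 = 16.3; at $40,000, 0.0124/0.003 = 4.1.
- Log for both: the divisor is ln(0.153/0.150) = 0.0198, giving 2.46 and 0.63.

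None of the log-link ratios is in dollars per QALY.

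**The case against.** Several objections have force.

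- *The stray sentence is editorial.* The extrapolated paragraph already names the model, horizon, discounting and correct ratio, and a health economist will support the analysis. It is probably a wording slip. It is still a stated rule that conflicts with its own paragraph. That the coefficients merely feed the Markov model is possible, but the sentence follows the ICER definition and does not say so.
- *Intervals are promised.* The plan refers to ICER point estimates in the plural, has two ICERs, and calls the within-trial sensitivity analysis probabilistic. A reader might infer that no interval is planned for the within-trial ICER; the text does not support that. What it supports is that the interval is not clearly assigned. On either reading, hospital and period are not mentioned.
- *Additive models satisfy both within-trial sentences.* This is correct. A reader might infer from "We will test different distribution parameters to determine the optimal distribution family for each model and outcome variable (e.g., binomial, gamma distributions") that costs will be log-linked and the ICER will be on the wrong scale. That sentence concerns Aim 1 outcomes, a gamma family does not fix a link, and Aim 2 chooses none. The scale is unstated, not shown to be wrong.

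Two stronger readings of the arithmetic also fail. One is that 10-15% variation can move the ICER only by about −15% to +18% and never change its sign. That holds only if a whole increment is scaled. The plan varies inputs, and its own account has programme costs offset by savings, so larger shifts and sign changes are possible, as shown above. The other is that the SE ratios measure an error in the planned analysis. The pooled comparator is not proposed anywhere in the documents, and part of the inflation comes from period adjustment alone.

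**Conclusion.** The concern holds in limited form and should be corrected before the Aim 2 analysis.

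- **Firm:** the coefficient rule does not fit the Markov-based 12-month ICER, and Aim 2 is silent on hospital clustering and calendar period.
- **Firm apart from one ambiguity:** the only uncertainty method clearly attached to the within-trial ICER is 10-15% input variation; the plural wording of the interval sentence leaves some doubt about its reach.
- **Conditional:** the within-trial coefficient ratio is an ICER only on additive scales, and the link is unstated.

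The size of any error in the reported ICER cannot be estimated from the documents. The SE ratios of 1.43-1.69 (1.42-2.14 with autocorrelation 0.8) rest on equal cells and assumed ICCs. They show only that an interval must account for hospital and period together.

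**What to change.** **Extrapolated section.** Delete the coefficient sentence. State that the ICER is the difference between strategies in model-expected discounted 12-month costs, divided by the difference in model-expected discounted 12-month QALYs.

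**Within-trial section.** Compute the ICER from model-predicted mean differences in dollars and in QALYs, which gives the right scale whatever link is used. Add a joint cost-QALY interval and an acceptability curve that account for hospital and four-month period, with a small-sample correction for eight hospitals. One option is net-benefit regression: for each willingness-to-pay value λ, form λ × QALYs − cost for each patient and fit a linear mixed model with fixed period and random hospital. Alternatively, extend the existing interval sentence explicitly to the within-trial ICER in that form. Keep the 10-15% variation as an additional sensitivity analysis.

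**Cost.** Changes to the SAP text and somewhat more analysis work, with no new data collection. The reported within-trial interval may be wide.
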